Appendix 5: RGI-C Data Collection Form

REGIONAL RATING OF RICKETS

How would you rate the change in XLH-related rickets in the HANDS/WRISTS? *Circle one*

-3	-2	-1	0	+1	+2	+3
Severe Worsening	Moderate Worsening	Minimal Worsening	No Change	Minimal Healing	Substantial Healing	Complete or Near Complete Healing

Identify abnormalities in image **A** on the left and then rate any change seen in image **B** on the right compared to image **A**

PA HAND/WRIST SINGLE ABNORMALITY RATING

BILATERAL PA RADIUS		NOT in "A"	DECREASED	UNCHANGED	INCREASED
	Metaphyseal lucency				
	Metaphyseal/epiphyseal separation				
	Metaphyseal fraying				
	Metaphyseal concavity				
BILATERAL PA Ulna		NOT in "A"	DECREASED	UNCHANGED	INCREASED
	Metaphyseal lucency				
	Metaphyseal/epiphyseal separation				
	Metaphyseal fraying				
	Metaphyseal concavity				

REGIONAL RATING OF RICKETS

How would you rate the change in XLH-related rickets in the KNEES? *Circle one*

-3	-2	-1	0	+1	+2	+3
Severe Worsening	Moderate Worsening	Minimal Worsening	No Change	Minimal Healing	Substantial Healing	Complete or Near Complete Healing

Identify abnormalities in image **A** on the left and then rate any change seen in image **B** on the right compared to image **A**

AP KNEES SINGLE ABNORMALITY RATING

BILATERAL AP FEMUR	NOT in "A"	DECREASED	UNCHANGED	INCREASED
Metaphyseal lucency				
Metaphyseal/epiphyseal separation				
Metaphyseal fraying				
Metaphyseal concavity				

AP KNEES SINGLE ABNORMALITY RATING

BILATERAL AP TIBIA	NOT in "A"	DECREASED	UNCHANGED	INCREASED
Metaphyseal lucency				
Metaphyseal/epiphyseal separation				
Metaphyseal fraying				
Metaphyseal concavity				

BILATERAL AP FIBULA	NOT in "A"	DECREASED	UNCHANGED	INCREASED
Metaphyseal lucency				
Metaphyseal/epiphyseal separation				
Metaphyseal fraying				
Metaphyseal concavity				

GLOBAL RATING OF RICKETS

How would you rate the change in XLH-related rickets?

The **B** images on the right as compared to **A** images on the left show *circle one*

-3	-2	-1	0	+1	+2	+3
Severe Worsening	Moderate Worsening	Minimal Worsening	No Change	Minimal Healing	Substantial Healing	Complete or Near Complete Healing

RATING OF LOWER LIMB DEFORMITY

How would you rate the change in XLH-related lower limb deformity? *Circle one*

-3	-2	-1	0	+1	+2	+3
Severe Worsening	Moderate Worsening	Minimal Worsening	No Change	Minimal Healing	Substantial Healing	Complete or Near Complete Healing

[figure not shown]
Identify abnormalities in image **A** on the left and then rate any change seen in image **B** on the right compared to image **A**

SINGLE ABNORMALITY RATING

[figure not shown]
STANDING LONG LEG	NOT in "A"	VARUS	VALGUS	DECREASED	UNCHANGED	INCREASED
L Tibia						
R Tibia						
L Fibula						
R Fibula						
L Femur						
R Femur						

Appendix 6: Blood Pressure Percentiles by Gender, Age and Height (NHLBI 2005)

Appendix 7: Heart Rate Percentiles by Gender and Age

Appendix 8: Events to Monitor

Injection site reactions: based on HLT “Injection site reaction”

Category	PT
Injection site reaction	Embolia cutis medicamentosa
Injection site reaction	Injected limb mobility decreased
Injection site reaction	Injection site abscess
Injection site reaction	Injection site abscess sterile
Injection site reaction	Injection site anaesthesia
Injection site reaction	Injection site atrophy
Injection site reaction	Injection site bruising
Injection site reaction	Injection site calcification
Injection site reaction	Injection site cellulitis
Injection site reaction	Injection site coldness
Injection site reaction	Injection site cyst
Injection site reaction	Injection site dermatitis
Injection site reaction	Injection site discharge
Injection site reaction	Injection site discolouration
Injection site reaction	Injection site discomfort
Injection site reaction	Injection site dryness
Injection site reaction	Injection site dysaesthesia
Injection site reaction	Injection site eczema
Injection site reaction	Injection site erosion
Injection site reaction	Injection site erythema
Injection site reaction	Injection site exfoliation
Injection site reaction	Injection site extravasation
Injection site reaction	Injection site fibrosis
Injection site reaction	Injection site granuloma
Injection site reaction	Injection site haematoma
Injection site reaction	Injection site haemorrhage
Injection site reaction	Injection site hyperaesthesia
Injection site reaction	Injection site hypersensitivity
Injection site reaction	Injection site hypertrichosis
Injection site reaction	Injection site hypertrophy
Injection site reaction	Injection site hypoesthesia
Injection site reaction	Injection site induration
Injection site reaction	Injection site infection
Injection site reaction	Injection site inflammation
Injection site reaction	Injection site injury
Injection site reaction	Injection site irritation
Injection site reaction	Injection site ischaemia
Injection site reaction	Injection site joint discomfort

Category	PT
Injection site reaction	Injection site joint effusion
Injection site reaction	Injection site joint erythema
Injection site reaction	Injection site joint infection
Injection site reaction	Injection site joint inflammation
Injection site reaction	Injection site joint movement impairment
Injection site reaction	Injection site joint pain
Injection site reaction	Injection site joint swelling
Injection site reaction	Injection site joint warmth
Injection site reaction	Injection site laceration
Injection site reaction	Injection site lymphadenopathy
Injection site reaction	Injection site macule
Injection site reaction	Injection site mass
Injection site reaction	Injection site movement impairment
Injection site reaction	Injection site necrosis
Injection site reaction	Injection site nerve damage
Injection site reaction	Injection site nodule
Injection site reaction	Injection site oedema
Injection site reaction	Injection site pain
Injection site reaction	Injection site pallor
Injection site reaction	Injection site papule
Injection site reaction	Injection site paraesthesia
Injection site reaction	Injection site phlebitis
Injection site reaction	Injection site photosensitivity reaction
Injection site reaction	Injection site plaque
Injection site reaction	Injection site pruritus
Injection site reaction	Injection site pustule
Injection site reaction	Injection site rash
Injection site reaction	Injection site reaction
Injection site reaction	Injection site recall reaction
Injection site reaction	Injection site scab
Injection site reaction	Injection site scar
Injection site reaction	Injection site streaking
Injection site reaction	Injection site swelling
Injection site reaction	Injection site thrombosis
Injection site reaction	Injection site ulcer
Injection site reaction	Injection site urticarial
Injection site reaction	Injection site vasculitis
Injection site reaction	Injection site vesicles
Injection site reaction	Injection site warmth
Injection site reaction	Malabsorption from injection site

Immunogenicity: based on relevant PTs in the narrow SMQs for “Hypersensitivity”

Category	PT
Hypersensitivity	Acute generalised exanthematous pustulosis
Hypersensitivity	Administration site dermatitis
Hypersensitivity	Administration site eczema
Hypersensitivity	Administration site hypersensitivity
Hypersensitivity	Administration site rash
Hypersensitivity	Administration site recall reaction
Hypersensitivity	Administration site urticaria
Hypersensitivity	Administration site vasculitis
Hypersensitivity	Allergic bronchitis
Hypersensitivity	Allergic colitis
Hypersensitivity	Allergic cough
Hypersensitivity	Allergic cystitis
Hypersensitivity	Allergic eosinophilia
Hypersensitivity	Allergic gastroenteritis
Hypersensitivity	Allergic granulomatous angiitis
Hypersensitivity	Allergic hepatitis
Hypersensitivity	Allergic keratitis
Hypersensitivity	Allergic myocarditis
Hypersensitivity	Allergic oedema
Hypersensitivity	Allergic otitis externa
Hypersensitivity	Allergic otitis media
Hypersensitivity	Allergic pharyngitis
Hypersensitivity	Allergic respiratory disease
Hypersensitivity	Allergic respiratory symptom
Hypersensitivity	Allergic sinusitis
Hypersensitivity	Allergic transfusion reaction
Hypersensitivity	Allergy alert test positive
Hypersensitivity	Allergy test positive
Hypersensitivity	Allergy to immunoglobulin therapy
Hypersensitivity	Allergy to vaccine
Hypersensitivity	Alveolitis allergic
Hypersensitivity	Anaphylactic reaction
Hypersensitivity	Anaphylactic shock
Hypersensitivity	Anaphylactic transfusion reaction
Hypersensitivity	Anaphylactoid reaction
Hypersensitivity	Anaphylactoid shock
Hypersensitivity	Anaphylaxis treatment
Hypersensitivity	Angioedema
Hypersensitivity	Antiallergic therapy
Hypersensitivity	Antidiomysial antibody positive
Hypersensitivity	Anti-neutrophil cytoplasmic antibody positive vasculitis
Hypersensitivity	Application site dermatitis
Hypersensitivity	Application site eczema
Hypersensitivity	Application site hypersensitivity

Category	PT
Hypersensitivity	Application site rash
Hypersensitivity	Application site recall reaction
Hypersensitivity	Application site urticaria
Hypersensitivity	Application site vasculitis
Hypersensitivity	Arthritis allergic
Hypersensitivity	Atopy
Hypersensitivity	Blepharitis allergic
Hypersensitivity	Blood immunoglobulin E abnormal
Hypersensitivity	Blood immunoglobulin E increased
Hypersensitivity	Bromoderma
Hypersensitivity	Bronchospasm
Hypersensitivity	Catheter site dermatitis
Hypersensitivity	Catheter site eczema
Hypersensitivity	Catheter site hypersensitivity
Hypersensitivity	Catheter site rash
Hypersensitivity	Catheter site urticaria
Hypersensitivity	Catheter site vasculitis
Hypersensitivity	Chronic eosinophilic rhinosinusitis
Hypersensitivity	Chronic hyperplastic eosinophilic sinusitis
Hypersensitivity	Circulatory collapse
Hypersensitivity	Circumoral oedema
Hypersensitivity	Conjunctival oedema
Hypersensitivity	Conjunctivitis allergic
Hypersensitivity	Corneal oedema
Hypersensitivity	Cutaneous vasculitis
Hypersensitivity	Dennie-Morgan fold
Hypersensitivity	Dermatitis
Hypersensitivity	Dermatitis acneiform
Hypersensitivity	Dermatitis allergic
Hypersensitivity	Dermatitis atopic
Hypersensitivity	Dermatitis bullous
Hypersensitivity	Dermatitis contact
Hypersensitivity	Dermatitis exfoliative
Hypersensitivity	Dermatitis exfoliative generalised
Hypersensitivity	Dermatitis herpetiformis
Hypersensitivity	Dermatitis infected
Hypersensitivity	Dermatitis psoriasiform
Hypersensitivity	Distributive shock
Hypersensitivity	Documented hypersensitivity to administered product
Hypersensitivity	Drug cross-reactivity
Hypersensitivity	Drug eruption
Hypersensitivity	Drug hypersensitivity
Hypersensitivity	Drug provocation test
Hypersensitivity	Drug reaction with eosinophilia and systemic symptoms
Hypersensitivity	Eczema
Hypersensitivity	Eczema infantile

Category	PT
Hypersensitivity	Eczema nummular
Hypersensitivity	Eczema vaccinatum
Hypersensitivity	Eczema vesicular
Hypersensitivity	Eczema weeping
Hypersensitivity	Encephalitis allergic
Hypersensitivity	Encephalopathy allergic
Hypersensitivity	Epidermal necrosis
Hypersensitivity	Epidermolysis
Hypersensitivity	Epidermolysis bullosa
Hypersensitivity	Epiglottic oedema
Hypersensitivity	Erythema multiforme
Hypersensitivity	Erythema nodosum
Hypersensitivity	Exfoliative rash
Hypersensitivity	Eye allergy
Hypersensitivity	Eye oedema
Hypersensitivity	Eye swelling
Hypersensitivity	Eyelid oedema
Hypersensitivity	Face oedema
Hypersensitivity	Giant papillary conjunctivitis
Hypersensitivity	Gingival oedema
Hypersensitivity	Gingival swelling
Hypersensitivity	Gleich's syndrome
Hypersensitivity	Haemorrhagic urticaria
Hypersensitivity	Hand dermatitis
Hypersensitivity	Henoch-Schonlein purpura
Hypersensitivity	Henoch-Schonlein purpura nephritis
Hypersensitivity	Hereditary angioedema
Hypersensitivity	Hypersensitivity
Hypersensitivity	Hypersensitivity vasculitis
Hypersensitivity	Idiopathic urticaria
Hypersensitivity	Immediate post-injection reaction
Hypersensitivity	Immune thrombocytopenic purpura
Hypersensitivity	Immune tolerance induction
Hypersensitivity	Infusion site dermatitis
Hypersensitivity	Infusion site eczema
Hypersensitivity	Infusion site hypersensitivity
Hypersensitivity	Infusion site rash
Hypersensitivity	Infusion site recall reaction
Hypersensitivity	Infusion site urticaria
Hypersensitivity	Infusion site vasculitis
Hypersensitivity	Injection site dermatitis
Hypersensitivity	Injection site eczema
Hypersensitivity	Injection site hypersensitivity
Hypersensitivity	Injection site rash
Hypersensitivity	Injection site recall reaction
Hypersensitivity	Injection site urticaria

Category	PT
Hypersensitivity	Injection site vasculitis
Hypersensitivity	Instillation site hypersensitivity
Hypersensitivity	Instillation site rash
Hypersensitivity	Instillation site urticaria
Hypersensitivity	Interstitial granulomatous dermatitis
Hypersensitivity	Intestinal angioedema
Hypersensitivity	Iodine allergy
Hypersensitivity	Kaposi's varicelliform eruption
Hypersensitivity	Kounis syndrome
Hypersensitivity	Laryngeal oedema
Hypersensitivity	Laryngitis allergic
Hypersensitivity	Laryngospasm
Hypersensitivity	Laryngotracheal oedema
Hypersensitivity	Limbal swelling
Hypersensitivity	Lip oedema
Hypersensitivity	Lip swelling
Hypersensitivity	Mast cell degranulation present
Hypersensitivity	Mouth swelling
Hypersensitivity	Mucocutaneous rash
Hypersensitivity	Multiple allergies
Hypersensitivity	Nephritis allergic
Hypersensitivity	Nikolsky's sign
Hypersensitivity	Nodular rash
Hypersensitivity	Oculomucocutaneous syndrome
Hypersensitivity	Oculorespiratory syndrome
Hypersensitivity	Oedema mouth
Hypersensitivity	Oral allergy syndrome
Hypersensitivity	Oropharyngeal blistering
Hypersensitivity	Oropharyngeal spasm
Hypersensitivity	Oropharyngeal swelling
Hypersensitivity	Palatal oedema
Hypersensitivity	Palatal swelling
Hypersensitivity	Palisaded neutrophilic granulomatous dermatitis
Hypersensitivity	Palpable purpura
Hypersensitivity	Pathergy reaction
Hypersensitivity	Periorbital oedema
Hypersensitivity	Pharyngeal oedema
Hypersensitivity	Pruritus allergic
Hypersensitivity	Radioallergosorbent test positive
Hypersensitivity	Rash
Hypersensitivity	Rash erythematous
Hypersensitivity	Rash follicular
Hypersensitivity	Rash generalised
Hypersensitivity	Rash macular
Hypersensitivity	Rash maculo-papular
Hypersensitivity	Rash maculovesicular

Category	PT
Hypersensitivity	Rash morbilliform
Hypersensitivity	Rash neonatal
Hypersensitivity	Rash papulosquamous
Hypersensitivity	Rash pruritic
Hypersensitivity	Rash pustular
Hypersensitivity	Rash rubelliform
Hypersensitivity	Rash scarlatiniform
Hypersensitivity	Rash vesicular
Hypersensitivity	Reaction to azo-dyes
Hypersensitivity	Reaction to colouring
Hypersensitivity	Reaction to drug excipients
Hypersensitivity	Reaction to preservatives
Hypersensitivity	Red man syndrome
Hypersensitivity	Rhinitis allergic
Hypersensitivity	Scleral oedema
Hypersensitivity	Scleritis allergic
Hypersensitivity	Scrotal oedema
Hypersensitivity	Serum sickness
Hypersensitivity	Serum sickness-like reaction
Hypersensitivity	Shock
Hypersensitivity	Shock symptom
Hypersensitivity	Skin necrosis
Hypersensitivity	Skin reaction
Hypersensitivity	Skin test positive
Hypersensitivity	Solar urticaria
Hypersensitivity	Solvent sensitivity
Hypersensitivity	Stevens-Johnson syndrome
Hypersensitivity	Stoma site hypersensitivity
Hypersensitivity	Stoma site rash
Hypersensitivity	Swelling face
Hypersensitivity	Swollen tongue
Hypersensitivity	Tongue oedema
Hypersensitivity	Toxic epidermal necrolysis
Hypersensitivity	Toxic skin eruption
Hypersensitivity	Tracheal oedema
Hypersensitivity	Type I hypersensitivity
Hypersensitivity	Type II hypersensitivity
Hypersensitivity	Type III immune complex mediated reaction
Hypersensitivity	Type IV hypersensitivity reaction
Hypersensitivity	Urticaria
Hypersensitivity	Urticaria cholinergic
Hypersensitivity	Urticaria chronic
Hypersensitivity	Urticaria contact
Hypersensitivity	Urticaria papular
Hypersensitivity	Urticaria physical
Hypersensitivity	Urticaria pigmentosa

Category	PT
Hypersensitivity	Urticaria vesiculosa
Hypersensitivity	Vaginal exfoliation
Hypersensitivity	Vaginal ulceration
Hypersensitivity	Vasculitic rash
Hypersensitivity	Vessel puncture site rash
Hypersensitivity	Vulval ulceration
Hypersensitivity	Vulvovaginal rash
Hypersensitivity	Vulvovaginal ulceration

Hyperphosphatemia: based on selected PTs below

Category	PT
Hyperphosphatemia	Hyperphosphatemia
Hyperphosphatemia	Blood phosphorus increased
Hyperphosphatemia	Blood phosphate abnormal

Ectopic mineralization: based on a MedDRA search of 'calcification'

Category	PT
Ectopic calcification	Adrenal calcification
Ectopic calcification	Aortic calcification
Ectopic calcification	Aortic valve calcification
Ectopic calcification	Aortic valve sclerosis
Ectopic calcification	Articular calcification
Ectopic calcification	Bladder wall calcification
Ectopic calcification	Breast calcifications
Ectopic calcification	Bursa calcification
Ectopic calcification	Calcific deposits removal
Ectopic calcification	Calcification metastatic
Ectopic calcification	Calcification of muscle
Ectopic calcification	Calcinosis
Ectopic calcification	Calculus bladder
Ectopic calcification	Calculus prostatic
Ectopic calcification	Calculus ureteric
Ectopic calcification	Calculus urethral
Ectopic calcification	Calculus urinary
Ectopic calcification	Cardiac valve sclerosis
Ectopic calcification	Cerebral calcification
Ectopic calcification	Chondrocalcinosis
Ectopic calcification	Chondrocalcinosis pyrophosphate
Ectopic calcification	Cutaneous calcification
Ectopic calcification	Dystrophic calcification
Ectopic calcification	Heart valve calcification

Category	PT
Ectopic calcification	Heart valve stenosis
Ectopic calcification	Hepatic calcification
Ectopic calcification	Intervertebral disc calcification
Ectopic calcification	Intestinal calcification
Ectopic calcification	Ligament calcification
Ectopic calcification	Lymph node calcification
Ectopic calcification	Mitral valve calcification
Ectopic calcification	Mitral valve sclerosis
Ectopic calcification	Myocardial calcification
Ectopic calcification	Nephrocalcinosis
Ectopic calcification	Nephrolithiasis
Ectopic calcification	Ovarian calcification
Ectopic calcification	Pancreatic calcification
Ectopic calcification	Pericardial calcification
Ectopic calcification	Pleural calcification
Ectopic calcification	Prostatic calcification
Ectopic calcification	Pulmonary calcification
Ectopic calcification	Pulmonary valve calcification
Ectopic calcification	Pulmonary valve sclerosis
Ectopic calcification	Splenic calcification
Ectopic calcification	Stag horn calculus
Ectopic calcification	Tendon calcification
Ectopic calcification	Tracheal calcification
Ectopic calcification	Tricuspid valve calcification
Ectopic calcification	Tricuspid valve sclerosis
Ectopic calcification	Vascular calcification

Restless legs syndrome

Category	PT
Restless legs syndrome	Restless legs syndrome
Restless legs syndrome	Restlessness
Restless legs syndrome	Akathisia
Restless legs syndrome	Psychomotor hyperactivity
Restless legs syndrome	Sensory disturbance
Restless legs syndrome	Muscle cramp
Restless legs syndrome	Limb discomfort
Restless legs syndrome	Neuromuscular pain
Restless legs syndrome	Formication

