3.2 Dosage and Administration

The length of this study will be 64 weeks. All subjects will receive KRN23 at a starting dose of 0.8 mg/kg every two weeks (Q2W). The dose may be increased to 1.2 mg/kg at any time if a subject meets the following dose adjustment criteria: 1) two consecutive serum phosphorus measurements are below the normal range; 2) serum phosphorus has increased by < 0.5 mg/dL from baseline; and 3) the subject has not missed a dose of study drug that would account for the decrease in serum phosphorus.

At any time during the study, if serum phosphorus increases above the upper limit of normal for age, the subsequent dose(s) will be withheld and the site will contact the medical monitor before dosing resumes. Once other causes of increased serum phosphorus are excluded, KRN23 treatment will resume at half the total dose of the last dose received. Serum phosphorus will be followed through unscheduled serum phosphorus assessments. A subject will resume dosing at the previous full total dose level if they meet the same dose-adjustment criteria listed above.

Serum phosphorus assessments will be conducted at the clinic at the ends of Weeks 1, 4, 8, 12, 15, 20, 32, 40, 48, 56 and 64. Growth (recumbent length/standing height) assessment will be conducted at the ends of Week 12, 24, 40 and 64. Bilateral AP knee X-rays, bilateral PA hand/wrist X-rays and standing long leg X-rays will be conducted at Week 40 and 64. The schedule of assessments is shown in [Appendix 3](#).

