3.5 Sample Size Considerations

The study will enroll approximately 10 pediatric subjects between 1 and 4 years old, inclusive, with clinical findings consistent with XLH including hypophosphatemia and radiographic evidence of rickets (at least 5 subjects will have a rickets severity score (RSS) at the knee of ≥ 1.5 points at Screening), and a confirmed *PHEX* mutation or variant of uncertain significance. To maintain a level of gender balance, no more than 7 subjects of either gender will be enrolled.

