5.9 Events to Monitor

The definition for each type of adverse events to monitor is as follows:

- Injection Site Reaction is defined by preferred terms under the Medical Dictionary for Regulatory Activities (MedDRA) high-level term (HLT) “Injection site reaction”.
- Immunogenicity AE: Defined using relevant PTs in the narrow SMQs for “Hypersensitivity”.
- Hyperphosphatemia AE: Defined by using PTs: “Hyperphosphataemia”, “Blood phosphorus increased”, “Blood phosphorus abnormal”.
- Ectopic calcification related AE: There is no available SMQ. Ectopic calcification related AE is defined using a MedDRA search of ‘calcification’.
- Restless leg syndrome AE: Defined by PTs “Restless legs syndrome”, “Restlessness”, “Akathisia”, “Sensory disturbance”, “Psychomotor hyperactivity”, “Limb discomfort”, “Neuromuscular pain”, “Formication”.

Please see the search criteria in [Appendix 8](#) for more details.

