8.10.1 Adverse Events

Adverse events will be coded by system organ class and preferred term using the MedDRA version 18.1 or the latest version at the time of snapshot/database lock. An AE (classified by preferred term) will be considered as a treatment emergent adverse event (TEAE) if it occurred on or after the first dose and was not present prior to the first dose, or it was present at the first dose but increased in severity during the study.

An overall summary table of AEs will be presented that will summarize the frequency and percentage of subjects who experienced any AE, events to monitor, experienced any TEAE, experienced a treatment-related TEAE, a treatment-emergent SAE, discontinued from study or from study drug treatment due to a TEAE, and experienced an AE leading to death. For this purpose, a treatment-related AE is defined as an AE that is either definitely, possibly or probably related to study medication.

Subject incidence of TEAEs will be tabulated in the following manner: by system organ class/preferred term, by system organ class/preferred term/relationship to study drug, by system organ class/preferred term/severity, and by preferred term for each event to monitor category. In addition, treatment-emergent SAEs, TEAEs leading to study discontinuations and TEAEs leading to death will be tabulated by system organ class/preferred term.

The incidence of injection site reactions will be summarized by study period to assess the trend over time. The summary of incidence over time may also be explored for other events to monitor categories.

Listings will be created for AEs which lead to death, discontinuation of treatment, and SAEs.

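### The hyperphosphatemia event list includes a preferred term with no direction, so a new or worsened low-phosphorus adverse event coded to it may be counted as hyperphosphatemia

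*SAP*

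**What the plan says.** Section 4.4 of the SAP names hyperphosphatemia as an event to monitor. The category is defined twice, each time by preferred terms alone.

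- Section 5.9 lists hyperphosphatemia, a term for increased blood phosphorus, and "Blood phosphorus abnormal".
- Appendix 8 introduces its table with "Hyperphosphatemia: based on selected PTs below" and lists hyperphosphatemia, "Blood phosphorus increased" and "Blood phosphate abnormal".

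Section 3.5 describes the children to be enrolled as having "clinical findings consistent with XLH including hypophosphatemia", and plans about 10 of them.

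Section 8.10.1 reports events to monitor in two main places. The overall adverse event summary has a line for them, and treatment-emergent events are tabulated "by preferred term for each event to monitor category". The same section says that incidence over time may also be explored for the categories other than injection site reactions.

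**The concern.** Two of the three terms point upward. The third records only that phosphorus was abnormal. Neither 5.9, Appendix 8 nor 8.10.1 links the event to the phosphorus result that prompted it, so the direction of an event coded to that term is never established.

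In most populations this would be a minor coding remark. Here the children start with low phosphorus and the drug is meant to raise it. High phosphorus would be overshoot, while low phosphorus is the disease itself. A category that can hold both may report a worsening of the disease as an excess drug effect. In a trial of this size a single event is visible in the reported percentage.

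The two lists also disagree on the wording of this very term, so the line has to be edited in any case.

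**Working it through.** The SAP gives no figure for this category, so there is nothing to reproduce. The check has two parts.

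**1. Which events the rule counts**

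| Adverse event as coded | On the 5.9 list? | On the Appendix 8 list? | Counted as hyperphosphatemia? |
|---|---|---|---|
| Hyperphosphatemia | yes | yes | yes |
| Blood phosphorus increased | yes | yes | yes |
| The non-directional *abnormal* term, value high | yes (phosphorus) | yes (phosphate) | yes, correctly |
| The non-directional *abnormal* term, value low | yes (phosphorus) | yes (phosphate) | yes, wrongly |
| A term naming a low or decreased value | no | no | no |

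Only the fourth row is a fault. It arises whichever wording is adopted, because both are silent on direction.

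The other places that could act as a filter are these:

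- Section 5.10 (dose-limiting toxicity) defines hyperphosphatemia by value, as a confirmed level of 6.5 mg/dL or more. It is a separate output and does not refer to the term list.
- Section 8.8.2 reports serum phosphorus by visit and the proportion in the normal range of 3.2 to 6.1 mg/dL. Section 8.10.2 counts abnormal laboratory results. Neither changes the count of events to monitor.
- Section 8.10.1 limits the preferred-term table to events that are new after the first dose or have increased in severity. That removes low phosphorus that was present at entry and is unchanged. It does not remove a new or worsened event. The overall summary lists events to monitor alongside treatment-emergent events without saying that the same restriction applies.

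**2. What one misclassified child does to the category**

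Inputs: N = 10 (Section 3.5, approximate), x children counted, exact (Clopper-Pearson) two-sided 95% interval.

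- Shift in incidence: 1/N = 1/10, or 10 percentage points.
- x = 0: the lower limit is 0. The upper limit is 1 − 0.025^(1/10) = 1 − 0.691503 = 0.308497, or 30.8%.
- x = 1: the lower limit is 1 − 0.975^(1/10) = 1 − 0.997471 = 0.002529, or 0.3%. The upper limit solves (1 − p)^10 + 10p(1 − p)^9 = 0.025, giving p = 0.445, or 44.5%.

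One such event therefore moves the category from 0/10 (0 to 30.8%) to 1/10 (0.3 to 44.5%). This shows the weight of a single event. It does not predict that one will occur.

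**The case against.** The strongest reply is that the list is a deliberately broad screen and that other outputs already guard against misreading.

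- **Breadth.** The other categories in Appendix 8 are also sensitive rather than specific: limb discomfort counts toward restless legs, and heart valve stenosis toward ectopic calcification. This is a fair reason to keep the term in the search. It does not justify counting an event that a result already collected shows to be the opposite.
- **Visibility.** The *abnormal* term would have its own row in the preferred-term table, and with about 10 children each such event can be followed up in the listings. That stands for the preferred-term table, although the row would not show direction. The overall summary has no stated breakdown by term.
- **Treatment-emergence.** Unchanged low phosphorus was present before the first dose, so it should not enter the preferred-term table. This stands, and it narrows the exposure to new or worsened events.
- **Direct measurement.** Overshoot can be read from the phosphorus values and from the dose-limiting toxicity definition. This also stands, but neither corrects the category count.

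A reader might infer that every low-phosphorus adverse event is counted as hyperphosphatemia. The lists do not support that, because an event coded to a term naming the low direction matches nothing on either one. A reader might also infer that the SAP expects children to remain low on treatment, since Section 3.2 speaks of the case where "two consecutive serum phosphorus measurements are below the normal range". That is a contingent criterion for dose adjustment and states no expectation.

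**Conclusion.** The point holds in a limited form. As written, the rule may count a new or worsened low-phosphorus adverse event as hyperphosphatemia if the event is coded to the non-directional term. The two definitions also word that term differently and need to be reconciled.

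The expected effect is small. The SAP gives no basis for estimating how often the term will be used, and the frequency is probably low. If it happens once, the incidence moves by 10 percentage points, assuming 10 children and no other event in the category. The value-based outputs are unaffected, so the documents do not support concluding that the trial's assessment of hyperphosphatemia as a whole is unreliable. The fault is confined to one named safety category, and it is worth correcting because the correction costs little.

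**What to change.** In Section 5.9 and Appendix 8:

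1. Use one wording for the non-directional term in both lists.
2. Keep the term in the search. Count an event coded to it as hyperphosphatemia unless the serum phosphorus result behind it is shown not to be above the upper limit of normal for age used by the laboratory.
3. Name that limit in the SAP. The document currently refers to an upper limit of normal for age (3.2), a range ending at 6.1 mg/dL (8.8.2) and a threshold of 6.5 mg/dL (5.10). Without a named limit, a value between 6.1 and 6.5 mg/dL could be classified either way.
4. If no value can be traced after a query, keep the event in the category and flag it, so that no true high event is lost.
5. Leave the two directional terms unchanged.

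An event shown not to be high stays in the general adverse event tables. The cost is a short addition to the SAP and one check against phosphorus results already collected, possibly with one query, for each event coded to this term.
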